## **2.0 STUDY POPULATIONS**

### **2.1 DEFINITIONS OF POPULATIONS FOR ANALYSIS**

The analysis sets will be defined as specified in Sections 2.1.1 through Section 2.1.3.

#### **2.1.1 Intent-to-Treat Analysis Set**

The intent-to-treat (ITT) analysis set will include all enrolled subjects who received at least one dose of study treatment. This analysis set will be used for all baseline characteristics and efficacy analyses.

#### **2.1.2 Per Protocol Analysis Set**

Although planned in the protocol, the per protocol analysis will not be conducted as determined by the sponsor.

#### **2.1.3 Safety Analysis Set**

The safety analysis set will include all subjects who received at least one dose of study drug. This analysis set will be used for all safety analyses.

As defined in the protocol, the ITT analysis set and safety analysis set are identical. Subjects who only receive one dose of study drug and do not return for any post-baseline visits will be included in the ITT analysis set, although they only provide data for safety assessments and no efficacy measurements.

### 3.0 STATISTICAL ANALYSIS

#### 3.1 GENERAL

Descriptive statistical methods will be used to summarize the data from this study. Unless stated otherwise, the term *descriptive statistics* refers to number of subjects with nonmissing data (n), mean, median, standard deviation, minimum, and maximum (with quartiles, 10th and 90th percentile) for continuous data and frequencies and percentages for categorical data.

Appendix listings of data from this study will also be provided.

█ [REDACTED]

[REDACTED]

[REDACTED]

[REDACTED]

[REDACTED]

#### 3.3 METHODS FOR HANDLING DROPOUTS AND MISSING DATA

Data will be analyzed as recorded. There will be no imputations conducted for missing data. Data will be analyzed at the visit at which the investigator assigned the data, even if the visit occurred outside of a visit window for that visit. Analyses using longitudinal models will implicitly use available data to inform the analysis of missing data, but no data will be explicitly imputed.

#### 3.4 BASELINE VALUES

The baseline value will be defined as the last nonmissing value on or before the baseline visit (Day 1).

#### **4.0 SUBJECT ENROLLMENT AND DISPOSITION**

The following will be summarized with frequencies and percentages of subjects in safety analysis set: subject enrollment (subjects enrolled who signed ICF); inclusion in analysis sets (ITT and safety analysis sets); number of subjects completing the study; number of subjects discontinuing the study before study completion; reasons for premature discontinuation; and the number of days on study. The number of subjects discontinued by visit will also be presented.

Date and time of last dose will also be provided in a listing.

## **5.0 EVALUATION OF BASELINE MEASUREMENTS**

This section describes the analysis of all demographics, baseline characteristics, medical history, and tests performed as part of inclusion and exclusion criteria, evaluated at screening exclusively.

### **5.1 DEMOGRAPHICS AND BASELINE CHARACTERISTICS**

Demographic parameters (e.g., age [based on date of birth and date of signed informed consent form], sex, race, ethnicity, height, weight, body mass index [BMI]) and baseline characteristics (e.g., type of IBD, and Partial Mayo Risk score at baseline) will be summarized descriptively for the ITT analysis set. BMI is calculated as a person's weight in kilograms divided by height in meters squared ( $\text{kg}/\text{m}^2$ ). Demographic and baseline characteristic data will be summarized and listed for the safety analysis set.

### **5.2 MEDICAL HISTORY**

Medical history, including pre-treatment AEs, will be collected at the screening visit. Medical history will include all information on a subject until the first dose of study medication. Medical history data (medical history verbatim term, start date, end date or ongoing status at baseline) will be provided in an appendix listing for the safety analysis set.

### **5.3 SCREENING BLOOD TESTS**

At screening, blood will be drawn for infectious disease assessments (hepatitis B surface antigen, hepatitis C virus antibody, human immunodeficiency virus 1 and human immunodeficiency virus 2 antibodies, and anti-smooth muscle antibody. Infectious diseases assessments and anti-smooth muscle antibody data will be provided in a listing for the safety analysis set.

### **5.4 URINE DRUG SCREEN AND PREGNANCY TESTS**

A urine drug result will be collected at screening for amphetamines, barbiturates, cocaine, methadone, and opiates. For females of childbearing potential only, a urine pregnancy test (dipstick) and serum pregnancy test will be performed also at

screening. Urine drug screen data and pregnancy test data for enrolled subjects will be provided in an appendix listing for the safety analysis set.

## 6.0 EVALUATION OF TREATMENT EXPOSURE AND COMPLIANCE

All eligible subjects will receive 150 mg CVC daily for 24 weeks. CVC should be taken every morning with food. Study medication (i.e., CVC) will be supplied in a bottle containing 37 tablets for each subject, which is sufficient for 28 days of dosing. Study drug bottles are dispensed, and any unused medication and the medication bottles are returned at baseline (dispensed only) and at Week 4, Week 8, Week 12, Week 16, and Week 24 (returned only).

### 6.1 EXPOSURE TO TREATMENT

The treatment duration is calculated as the number of days from the date of the first dose of study medication taken to the date of last dose taken, inclusively. Descriptive statistics will be presented for the safety analysis set.

### 6.2 COMPLIANCE TO STUDY TREATMENT

Study medication dosing compliance for a *specified period* is defined as the total number of tablets taken by a subject during that period divided by the number of tablets expected to be taken during the same period multiplied by 100.

The number of tablets actually taken will be calculated by subtracting the tablets returned from the total number of tablets dispensed. The number of tablets expected to be taken for a specified period is the number of days in that period.

Descriptive statistics for the study medication compliance will be presented for each period between two consecutive visits, and over the 24 weeks (overall) for the safety analysis set.

## 7.0 EVALUATION OF EFFICACY PARAMETERS

This study will evaluate the effects of CVC in adult subjects with PSC. [REDACTED]

[REDACTED]

### 7.1 PRIMARY EFFICACY ENDPOINT

The primary endpoint for this study is the percent change from baseline through Week 24 in ALP.

The percent change from baseline will be calculated as follows:

$$ALP (\%) = \frac{(value\ at\ each\ visit - baseline\ value)}{baseline\ value} \times 100$$

[REDACTED]

[REDACTED]

If the normality and homogeneity of variance assumptions are significantly violated, then the baseline and percentage change from baseline parameters are first ranked separately, using the combined data from all visits. Tied values will receive the mean value (midranks) of the corresponding ranks. Then, the same mixed-

effect repeated measure model with ranked data will be used for the primary efficacy analyses.

### 7.1.1 Pre-treatment Change per Week with On-treatment Change per Week

Also a comparison of *pre-treatment change per week with on-treatment change per week* will be made through an estimate specification and the corresponding 95% confidence interval will be reported. To this end, a similar linear mixed-effect repeated measure model will be fit with change from baseline at the visit as the dependent variable, visits (baseline, Weeks 4, 8, 12, 16, and 24) as fixed factors, baseline score and baseline score-by-visit interaction as covariates, the visit nested within subject and subject as a random effect to model correlations among the within-subject repeated measures. A compound symmetry structure will be used initially in the model for the correlation pattern among the repeated measures. If this does not converge, then other covariance structure, for example, the spatial power covariance structure for unequally spaced time intervals will be used to model the repeated assessment over time. Denominator degrees of freedom will be estimated using the Kenward-Roger method.

Pre-treatment change from baseline is defined as follows:

$$\text{screening value} - \text{baseline value}$$

For multiple t-test, pairwise comparisons based on the Bonferroni adjusted t-test would produce comparisons of the group means for *on-treatment change* from baseline at the visit *back to pre-treatment change*. Through this model, two-sided 95% confidence intervals will be produced for comparisons of the group means at the visit (*on-treatment change*) back to the first time point (*pre-treatment change*).

Percent changes in ALP from baseline will be summarized using descriptive statistics for the respective pre-treatment and on-treatment visits.

The ALP raw values and the percent change from baseline in ALP at each visit will be summarized descriptively by visit: before treatment (screening, baseline) and during treatment (Weeks 2, 4, 8, 12, 16, and 24).

Descriptive comparisons will be made for the following:

- Subjects with a history of IBD vs. no history of no IBD at screening
- Subjects who received UDCA for at least 3 months before screening vs. who have not received UDCA for at least 3 months before screening

Figures for the percent changes in ALP from baseline by visit will also be presented.

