
Safety Evaluation
	
Safety endpoints:
 
 
• Evaluate the safety and tolerability of CVC through 24 weeks of treatment in adult subjects with PSC
 
• Evaluate the proportion of subjects with a treatment-emergent AE or a clinically significant laboratory abnormality (overall and of any given type)
 

	
 
• Evaluate the proportion of subjects who discontinue due to an AE
 

Other Exploratory Evaluation	
[REDACTED]
 
[REDACTED]
 
[REDACTED]
 
[REDACTED]
 
[REDACTED]

Statistical Analysis	
This is a single arm open label study in adult subjects with PSC. Descriptive statistical methods will be used to summarize data from this study. Displays of treatment-related efficacy and safety profiles for each patient and overall will be summarized.

Efficacy Analysis	
Percent changes in ALP from Baseline will be summarized using descriptive statistics for the respective pre-treatment and on-treatment visits. A repeated measures mixed model will be fit to the data for all pre-treatment and on-treatment visits, and this model will include explanatory variables for visits and Baseline; and it will have compound symmetry as the covariance structure. Through this model, 95% confidence intervals will be produced for the mean percent change at each visit. Also, a comparison of pre-treatment change per week with on-treatment change per week will be made through an estimate specification and the corresponding 95% confidence interval. Descriptive comparisons will be made with historical data where UDCA was administered and/or with the natural history of the disease, as appropriate.

Safety Analysis	
Clinical laboratory and safety data will be summarized using descriptive analysis.

Sample Size	
Each patient will serve as their own control when observing ALP relative to Baseline. [REDACTED]
 
[REDACTED]
 
[REDACTED]
 
[REDACTED]
 
[REDACTED]
 
[REDACTED]
 
[REDACTED]
 
[REDACTED]

[REDACTED]

[REDACTED]

[REDACTED]

[REDACTED]

[REDACTED]

[REDACTED]

[REDACTED]

[REDACTED]

[REDACTED]

[REDACTED]

[REDACTED]

[REDACTED]

[REDACTED]

[REDACTED]

[REDACTED]

[REDACTED]

[REDACTED]

[REDACTED]

[REDACTED]

[REDACTED]

[REDACTED]

[REDACTED]

[REDACTED]

[REDACTED]

[REDACTED]

[REDACTED]

[REDACTED]

[REDACTED]

[REDACTED]

[REDACTED]

[REDACTED]

[REDACTED]

[REDACTED]

[REDACTED]

[REDACTED]

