## 1.7 SCOPE OF PLAN

This statistical analysis plan (SAP) provides a more technical and detailed elaboration of the statistical analyses of the efficacy and safety data as outlined or specified in the final protocol of Study Protocol 652-205 (version dated 19 November 2015) and the most recent amendment (Version 3 dated [14 June 2016]). Specifications of tables, figures, and data listings are contained in a separate document.

This SAP will indicate the methods to be used to analyze the safety and efficacy data collected during the study and will supersede any statistical analyses specified in the protocol. The planned analyses identified in this SAP will be included in regulatory submissions and future manuscripts. Additional exploratory analyses, which are not defined in this SAP, will be labeled as such in any study report or regulatory submission.

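### SAP 7.1.1 combines random subject, random visit-within-subject and compound symmetry in one model, which is not identified as written and should carry a single covariance statement

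*SAP*

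**What the plan says.** SAP 7.1.1 describes a repeated-measures mixed model for change from baseline in ALP. Its fixed part has "visits (baseline, Weeks 4, 8, 12, 16, and 24) as fixed factors", with baseline and baseline-by-visit as covariates. Its random part is "the visit nested within subject and subject as a random effect to model correlations among the within-subject repeated measures".

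The next sentence adds a structure for the same correlations: "A compound symmetry structure will be used initially in the model for the correlation pattern among the repeated measures". The fallback follows: "If this does not converge, then other covariance structure, for example, the spatial power covariance structure for unequally spaced time intervals will be used". Inference is by Kenward-Roger ("Denominator degrees of freedom will be estimated using the Kenward-Roger method"), and "two-sided 95% confidence intervals will be produced for comparisons of the group means at the visit" relative to the first, pre-treatment, time point.

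The visible text of the protocol synopsis (Efficacy Analysis) is simpler. Its model has visits and baseline as explanatory variables, and "it will have compound symmetry as the covariance structure". It mentions no random effects and no fallback. SAP 1.7 states that the SAP "will supersede any statistical analyses specified in the protocol", so the SAP wording governs.

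The SAP does not say what counts as non-convergence, whether the random effects stay after a switch, or which structures would be tried and in what order. Spatial power is only an example.

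**The concern.** A random subject effect already produces compound symmetry. A random visit-within-subject effect with one observation per level cannot be separated from the residual. A compound-symmetry residual structure on top of both counts each component twice. The covariance parameters then have a singular information matrix, and Kenward-Roger relies on the inverse of that matrix.

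This would be mere untidiness if nothing depended on convergence. In this section, however, non-convergence is what changes the covariance structure. A failure caused by the specification, and not by the ALP data, could therefore decide which structure lies behind the reported intervals.

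**Working it through.** **Inputs from the documents.** n = 25 (SAP 1.4, Protocol 12.1). SD 25 percentage points, true mean 30%, limit 15%, power 0.80, two-sided 95% interval (Protocol 12.1). Six visit levels (SAP 7.1.1). Screening up to 6 weeks before baseline (SAP 1.6), so rows are placed at weeks -6, 4, 8, 12, 16 and 24.

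**Assumptions.** One record per subject and visit; no replicates are described. The within-subject correlation ρ is not given in the visible text; values from 0.3 to 0.8 are used, plus a correlation decaying at 0.95 per week. SD 25 is stated for percent change, while the 7.1.1 outcome is change from baseline. The absolute SEs below are therefore illustrative; the ratios do not depend on the SD.

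**The plan's own figure.** SE = 25/√25 = 5 and (30 - 15)/5 = 3. Power is Φ(3 - 1.96) = 0.851 by normal approximation and 0.821 by noncentral t. The stated 0.80 at n = 25 reproduces. It does not use the 7.1.1 model, for which the plan gives no figure.

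**Step 1: identifiability.** With J the 6 × 6 matrix of ones and I the identity, the literal model gives

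V = σ²(subject) J + σ²(visit in subject) I + σ(CS) J + σ²(residual) I = [σ²(subject) + σ(CS)] J + [σ²(visit in subject) + σ²(residual)] I.

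Only the two bracketed sums can be estimated. The information for parameters i and j is (n/2) tr(V⁻¹ Vᵢ V⁻¹ Vⱼ), where Vᵢ is the derivative of V.

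- At V = 312.5 J + 312.5 I (SD 25, ρ = 0.5), the scaled matrix for compound symmetry alone has eigenvalues 0.936 and 1.064: two parameters, rank 2.
- Duplicating each parameter doubles these to 1.87 and 2.13 and adds two zeros: four parameters, rank 2.
- Missing visits do not help, because submatrices of J and I have the same form.
- If visit-within-subject is read only as the repeated index, random subject plus compound symmetry is still three parameters at rank 2.
- The spatial-power fallbacks are identified: alone (2 of 2), with random subject (3 of 3), with both random terms (4 of 4).

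**Step 2: fitting it anyway.** REML fits from three starting points gave the same mean -2 restricted log-likelihood (1006.21 at ρ = 0.5) and the same SE for Week 24 minus the first time point (4.988). Both equal the values for compound symmetry alone. Only the split was arbitrary: the subject variance in one data set came out as 131, 276 and 20. In further simulated trials the over-parameterised model converged in 99-100%.

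**Step 3: what a switch would do.** Mean SEs over 20 simulated trials per scenario (visit and baseline-by-visit fixed effects). CS is compound symmetry, SP spatial power alone, S+SP random subject plus spatial power.

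| True structure | Week 24 minus first: CS | SP | S+SP | Per week: CS | SP | Week 24 mean: CS | SP |
|---|---|---|---|---|---|---|---|
| CS, ρ = 0.3 | 5.87 | 7.18 | 5.91 | 0.931 | 0.874 | 5.05 | 5.09 |
| CS, ρ = 0.5 | 4.99 | 6.89 | 5.02 | 0.932 | 0.855 | 4.90 | 4.95 |
| CS, ρ = 0.8 | 3.28 | 6.22 | 3.31 | 1.023 | 0.931 | 5.09 | 5.12 |
| Decay 0.95/week | 4.66 | 6.28 | 5.97 | 0.983 | 0.916 | 5.08 | 5.06 |

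- Week 24 minus first, SP to CS: mean ratios 1.22, 1.39, 1.90 and 1.35. At ρ = 0.5 the half-width goes from 1.96 × 4.99 = 9.8 to 1.96 × 6.89 = 13.5.
- The same contrast, S+SP to CS: about 1.01 under compound symmetry and 1.28 under decay.
- Per-week contrast, SP to CS: 0.91-0.94.
- Week 24 mean, SP to CS: 1.00-1.01.

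A larger set (300 trials per ρ) gave, for SP against CS on Week 24 minus first, 7.04/5.45 = 1.29, 7.01/5.02 = 1.40, 6.86/4.46 = 1.54 and 6.61/3.87 = 1.71 at ρ = 0.4, 0.5, 0.6 and 0.7. With random subject kept (100 trials per ρ, visit means only) the ratios were 1.007, 1.009, 1.009 and 1.009. Over that range of ρ the per-week SE under spatial power alone was about 7-10% smaller.

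**Step 4: why the contrasts move in opposite directions.** The SAP defines pre-treatment change as screening minus baseline. The difference in weekly rates is therefore (Week 24 row)/24 + (first row)/6, a sum. Spatial power alone shrinks the covariance between the two distant rows. That inflates a difference and deflates a sum. At ρ = 0.5, taking the same SE for both rows, the covariance is (2 × 4.904² - 4.988²)/2 = 11.61 under CS and (2 × 4.945² - 6.894²)/2 = 0.69 under SP. The per-week variance is SE²(1/24² + 1/6²) + 2 cov/(24 × 6). This is 0.710 + 0.161 = 0.871 under CS (SE 0.933) and 0.722 + 0.010 = 0.731 under SP (SE 0.855), in line with the table.

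**The case against.** The sponsor has good replies, and most of them limit the point.

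- **It may be loose prose for one structure.** Compound symmetry could simply name what the random subject effect induces, with visit within subject as the repeated index. That would match the synopsis. It is possible, but the SAP does not say so: it lists both terms as random and then adds a structure. The 7.1 model that this one is said to resemble is redacted and cannot settle the matter.
- **The switch changes the covariance structure and does not remove random effects.** On that reading the fallback keeps random subject, and under compound-symmetric data the SE moves about 1%. The 1.28 under decaying correlation is not an artefact, because compound symmetry would then be the wrong structure. This reply stands. The remaining fault is that the SAP leaves the question open.
- **A singular information matrix is not non-convergence.** This also stands. The over-parameterised fits nearly always converged and gave the right answer. The software name is redacted, so its behaviour cannot be checked.
- **A prespecified fallback is legitimate, and the SAP may supersede the protocol.** Agreed. Departing from the synopsis is not in itself a defect.
- **The stakes are low.** SAP 1.3 calls the aim exploratory and 7.1.1 is an additional comparison. The Week 24 mean, on which Protocol 12.1 rests, is practically unaffected.

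A reader might infer that the trial's intervals will come out 30-70% wider, or that the primary analysis is affected. The documents support neither. The first needs a reported failure, removal of the random terms at the switch, and the difference contrast; the section's title contrast becomes narrower instead. The second cannot be judged, because the 7.1 model text is redacted.

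**Conclusion.** The redundancy is exact: four covariance parameters, rank 2, given one record per subject and visit. The first-choice model in SAP 7.1.1 is not identified as written. The practical harm is conditional and probably small. Where the software converges or zeroes the surplus terms, nothing reported changes. Where it reports failure or a singular Hessian, the structure could be switched for a reason unrelated to the data. The result then depends on an unstated choice. For compound-symmetric data and assumed ρ of 0.4 to 0.7, the SE of Week 24 minus the first time point changes about 1% with random subject kept and rises about 30-70% with spatial power alone. In the latter case the per-week SE falls about 7-10% and the Week 24 mean hardly changes. These ratios rest on assumed correlations and simulated data. This is a minor correction to a supportive analysis, worth making because it costs nothing.

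**What to change.** In SAP 7.1.1, delete the clause that makes visit-within-subject and subject random effects. Use one covariance statement: compound symmetry on visit within subject, as in the protocol synopsis, with Kenward-Roger degrees of freedom. The fits above show that this loses nothing, since compound symmetry alone gives the same likelihood and SEs.

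Keep a prespecified fallback for genuine non-convergence of that identified model, and state that no extra random terms are added to it. Make the same edit in SAP 7.1 only if its redacted model carries the clause.

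The cost is a few lines of SAP text, with no effect on data, sample size or visits.

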### 10.1 Screening Visit

Prior to any clinical procedures and evaluations, written signed informed consent must be obtained. Screening is to occur approximately 6 weeks before the Baseline visit (see Section 10.2).

Subjects who do not meet all eligibility criteria at Screening will be allowed to rescreen once. However, if a subject fails to meet eligibility criteria upon rescreen, he or she will remain ineligible for the study.

At Screening Visit, the following Screening procedures and assessments should be conducted:

■ [REDACTED]

[REDACTED]

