### 10.2 Baseline Visit (Day 1)

Subjects who have signed the ICF and meet all the eligibility criteria (see Sections [8.2](#) and [8.3](#)) will be enrolled in the study. If subjects are deemed eligible once results from the Screening visit are received, Baseline visit can take place immediately or approximately within 6 weeks after the Screening visit.

[REDACTED]

[REDACTED]

- [REDACTED]
- [REDACTED]
- [REDACTED]
- [REDACTED]
- [REDACTED]
- [REDACTED]
- [REDACTED]
- [REDACTED]
- [REDACTED]
- [REDACTED]
- [REDACTED]
- [REDACTED]
- [REDACTED]
- [REDACTED]
- [REDACTED]
- [REDACTED]
- [REDACTED]
- [REDACTED]
- [REDACTED]
- [REDACTED]
- [REDACTED]
- [REDACTED]
- [REDACTED]
- [REDACTED]
- [REDACTED]

[REDACTED]

[REDACTED]

[REDACTED]

[REDACTED]

[REDACTED]

[REDACTED]

[REDACTED]

[REDACTED]

[REDACTED]

[REDACTED]

[REDACTED]

[REDACTED]

[REDACTED]

[REDACTED]

[REDACTED]

[REDACTED]

[REDACTED]

[REDACTED]

[REDACTED]

[REDACTED]

[REDACTED]

[REDACTED]

- █ [REDACTED]
- █ [REDACTED]

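### SAP 7.1.1 promises to compare ALP change per week before and on treatment, but the contrasts it writes out are undivided changes and are not zero under an unaltered trend

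*SAP*

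**What the plan says.** The Efficacy Analysis entry of the protocol synopsis states that "a comparison of pre-treatment change per week with on-treatment change per week will be made through an estimate specification", with a 95% confidence interval. SAP 7.1.1 repeats this in its title and opening sentence. To that end it fits a mixed model "with change from baseline at the visit as the dependent variable, visits (baseline, Weeks 4, 8, 12, 16, and 24) as fixed factors".

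It continues "Pre-treatment change from baseline is defined as follows", and the formula is screening minus baseline. Bonferroni-adjusted comparisons then take each visit back to pre-treatment change, and "two-sided 95% confidence intervals will be produced for comparisons of the group means at the visit" against what it calls the first time point, glossed as pre-treatment change.

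Four other provisions bear on the inputs:

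- **Baseline (SAP 3.4):** the last nonmissing value on or before Day 1.
- **Screening gap:** Protocol 10.1 says "Screening is to occur approximately 6 weeks before the Baseline visit", while Protocol 10.2 says "Baseline visit can take place immediately or approximately within 6 weeks after the Screening visit". The gap therefore varies by subject.
- **Rescreening (Protocol 10.1):** "Subjects who do not meet all eligibility criteria at Screening will be allowed to rescreen once".
- **Precedence (SAP 1.7):** the SAP overrides the protocol's analyses. The synopsis's broader model, which covers all pre-treatment visits, therefore does not fill the gap.

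**The concern.** In a single-arm study, a change from baseline mixes any drug effect with whatever ALP was already doing. A comparison of rates is meant to separate the two, and in the readable text this is the only model-based analysis with that purpose. It should give zero when the trend simply continues through Day 1.

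The contrasts written out do not have that property. Nothing in the section divides by weeks, and with no screening level in the visit factor the model as listed has no pre-treatment mean to use. A steady fall that CVC does not alter would be reported under a change-per-week heading as benefit, and a steady rise as harm.

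**Working it through.** SAP 7.1.1 states no number, so there is none to reproduce.

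**Algebra (no assumed SD or drift needed).** Let S be ALP at screening (g weeks before Day 1), B baseline and Y the value at Week t. Suppose one unbroken trend of b per week.

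- First time point read as screening: (Y − B) − (S − B) = Y − S = b(t + g). With g = 6 this is 10b, 14b, 18b, 22b and 30b at Weeks 4, 8, 12, 16 and 24.
- Visit list read literally, so that the first time point is baseline (change 0 by definition): Y − B = bt, that is 4b, 8b, 12b, 16b and 24b. No pre-treatment value enters.
- Forward comparison of rates: (Y − B)/t − (B − S)/g = b − b = 0 for every t and g.
- The SAP's sign divided by unsigned weeks: (Y − B)/t − (S − B)/g = b − (−b) = 2b.

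**Worked example** (invented ALP values, g = 6, t = 24):

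| Course per week | S | B | Y | Y − S | Y − B | Difference in rates |
|---|---|---|---|---|---|---|
| −2 throughout (no drug effect) | 300 | 288 | 240 | −60 | −48 | 0 |
| 0, then −2 on drug | 300 | 300 | 252 | −48 | −48 | −2 |
| +2, then −2 on drug | 300 | 312 | 264 | −36 | −48 | −4 |

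Visit minus screening ranks the three courses in the wrong order. Visit minus baseline cannot tell them apart.

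**Illustrative size.** Inputs are n = 25 and SD 25% (Protocol 12.1, stated for percent change, whereas 7.1.1 models raw change). The drift b is assumed, because the documents give none. SE = 25/√25 = 5%; noncentral t with 24 df; Week 24; g = 6. Each cell gives the chance that the interval excludes zero, unadjusted and then Bonferroni for 5 visits (0.05/5 = 0.01).

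| b, % of baseline per week | Visit − screening (mean 30b) | Visit − baseline (mean 24b) |
|---|---|---|
| 0.125 | 11%; 3% | 9%; 2% |
| 0.25 | 30%; 12% | 21%; 7% |
| 0.5 | 82%; 59% | 63%; 37% |

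At b = 0.5%, varying the SD from 30% to 20% gives unadjusted values of 67 to 95% and 48 to 82%. A simulation of a model of the SAP's type (compound symmetry, baseline covariate and interaction, 6,000 runs, b = ±0.5%) gave 84 to 85% and 66 to 67%. In the same simulation, with b of 0 or ±0.5% and both noise settings below, the forward rate estimate averaged within 0.02 of zero and excluded zero in 1 to 7% of runs.

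**Precision of the corrected estimate.** SE = √[s²(1/24² + (1/24 + 1/g)² + 1/g²)/25]. A subject's own slope cancels. Two assumed settings reproduce a 24-week SD of 25%: visit noise s = 10% with slope SD 0.86% per week (√(2·10² + (24·0.86)²) ≈ 25), or s = 17.7% with no slope variation (√2·17.7 ≈ 25).

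- g = 6: SE 0.54 to 0.96% of baseline per week.
- g = 2: SE 1.5 to 2.6%.
- Power at g = 6 for 30%/24 = 1.25% per week (the 30% is from Protocol 12.1): 60% down to 24%.

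**Regression to the mean.** Entry requires ALP of at least 1.5×ULN (Protocol 8.2), so screening values are selected high. Assumptions: lognormal ALP, median 2 to 3×ULN, between-subject log SD 0.4 to 0.5, within-subject log SD 0.10 to 0.25. Screening then exceeds baseline by 0.1 to 3.8% of baseline on average.

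- Visit minus screening gains that amount in the drug's favour. Visit minus baseline is hardly affected.
- The corrected estimate is biased against the drug by that amount divided by g: 0.02 to 0.63% per week at g = 6 (up to 0.63 × 24 ≈ 15% over 24 weeks), and up to 1.9% per week at g = 2.

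**The case against.** The strongest reply is that two analyses are being run together. The per-week comparison is assigned to an estimate specification that could carry 1/t and 1/g weights; the visit contrasts come later and are not labelled per week. It is true that the estimate is unspecified rather than shown to be wrong. But the model is introduced as the means to the per-week comparison, and with no screening level in its visit factor no estimate from it can recover a pre-treatment rate.

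Other points on that side:

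- **Drift affects any single-arm change from baseline, including the primary endpoint.** True. The visit-minus-baseline figures describe that exposure. The fault here is that the section meant to address it does not.
- **The literal reading of the visit list is strained, and the omission of screening is probably a slip.** Quite possibly. The other reading still gives b(t + g).
- **Screening minus baseline is correct if divided by signed time.** True. The 2b result arises only with unsigned weeks, but the SAP states neither.
- **The probabilities rest on assumed drift, and the stable-therapy entry criteria argue against a large one.** Fair. They are illustrations; with b = 0 both contrasts are zero.
- **The corrected estimate is weak and can be biased.** True, and it limits how the result may be used. It does not justify reporting a different quantity under the per-week heading.
- **A missing Day 1 ALP or a rescreen will be uncommon.** Agreed; these need one sentence each.
- **The text following the SAP 7.1 formula and part of Protocol 12.4.2 are blacked out.** The conclusion is therefore confined to 7.1.1, which shows no redaction.

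**Conclusion.** The concern holds. The contrasts written in SAP 7.1.1 equal b(t + g) or bt under an unaltered trend, so they do not compare rates of change. This follows from the definitions and needs only a non-zero b. How often it would mislead is unknown: the 82% and 63% depend on an assumed drift of 0.5% per week and a borrowed SD.

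Two inputs are also open. If there is no Day 1 ALP, the screening value can become baseline, giving a change of 0 over 0 weeks. The section also does not say which screening value counts after a rescreen.

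The reach is limited. This is a supporting comparison in a proof-of-concept study that SAP 1.3 describes as exploratory. The primary endpoint formula (SAP 7.1) and the responder endpoints (SAP 7.2) need no change, and the planned summaries of screening and baseline ALP would still show pre-dose drift descriptively. It should be fixed before the analysis is programmed.

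**What to change.** Amend SAP 7.1.1 as follows.

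1. Add screening as a visit level, and the pre-baseline visit for subjects enrolled under Amendments 1 and 2. The baseline level is zero by definition and can be dropped.
2. Define pre-treatment change as baseline minus screening.
3. Write out the estimate as (visit − baseline)/t − (baseline − screening)/g. On the model's own response (value minus baseline), the coefficients are +1/t on the visit mean and +1/g on the screening mean.
4. Use actual weeks and apply the weights to group means with the mean gap. Because baseline may follow screening at once, per-subject ratios are unstable: with gaps spread over 1 to 6 weeks the SE is 1.5 to 2.6% per week, against 0.88 to 1.6% with group means.
5. State which screening value counts after a rescreen, and leave subjects whose baseline is not a Day 1 value out of the pre-treatment part.
6. Label any visit contrasts that are kept as change from screening.
7. State that the estimate is supportive only, being imprecise and biased against the drug by regression to the mean. That bias may be material.

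A piecewise-linear model on actual weeks with a knot at Day 1 is an alternative. Either way the cost is SAP wording and programming, since the ALP values and dates are already collected.
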